5.8.4. Patient-Reported Outcomes

5.8.4.1. Symptoms of Infection with Coronavirus-19 (SIC)

The SIC is a disease-specific patient-reported outcome (PRO) instrument that is completed by the participant, self-administered. The SIC has a total of 30 items assessing signs and symptoms of COVID-19. The first 25 items, the participant indicates “yes” or “no” if they have a symptom and if “yes” report a severity from 0 (none) to 10 (worst possible). The second part has the participant enter their temperature, and the third part has the participant record “yes” or “no” (absence or presence of additional signs and symptoms). The analyses are conducted in two ways, by part 1, part 2 and part 3, scored separately, and also grouped into related categories for composite scoring :

SIC Analysis Approach One:

- Part 1 (25 symptoms): Each symptom is present or absent (0), and if present rated on a 10 point scale from ranging from 0 (None) to 10 (Worst possible).

The **symptom score** is the mean score of all items on the SIC for each day, during the COVID-19 episode.

The **symptom duration** is the period from the first day of symptoms till the last day with symptoms in Days (calculated as last day with symptoms – first day of symptoms + 1).

The **symptom AUC** is the area under the curve for the complete COVID-19 episode.

The **peak symptom score** is the maximum of all the symptom scores during the COVID-19 episode.

- Part 2: Fever/ temperature.

Fever will be scored (fever score) as the maximum recorded temperature for each day during the COVID-19 episode.

Fever will be coded as ‘Present’ if the fever score is $\geq 38.0\text{ }^{\circ}\text{C}$ or $\geq 100.4\text{ }^{\circ}\text{F}$ and ‘Absent’ otherwise.

The **total fever days** is the number of days with fever present during the COVID-19 episode.

Fever duration will be the period from the first day with fever till the last day with fever in Days (calculated as last day with fever – first day of fever + 1).

The **peak fever** is the maximum fever score during the COVID-19 episode.

The **fever AUC** is the AUC of fever score during the total of fever days of the COVID-19 episode. (For the AUC if there is a single missing day between days with fever the missing day will be ignored, i.e., interpolation will be used in the calculation of the AUC.)

The fever score will also be coded using FDA grades for fever.

Part 3: Each of the 3 specific symptoms is either present (1) or absent (2).

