The **specific symptom score** is the mean of all scores during the COVID-19 episode.

The **specific symptom duration** is the duration of specific symptoms during the COVID-19 episode from the first day with a specific symptom till the last day with a specific symptom in Days (calculated as last day with a specific symptom – first day of a specific symptom + 1).

The **total specific reported symptom score** is the mean of all scores during the COVID-19 episode at which a subject has reported at least one specific symptom.

Note 1: For Part 1, total scores will be calculated based on the number of assessments completed by the participant per day and in cases where more than 75% of the items needed to calculate the score is not collected (reported as no answer to the part 1 Yes/No possibility AND no severity rate), then the value for that score will be set to missing. For example, if a participant has responded to 7 or more out of the 25 symptom scale questions the score will be the mean of the available questions. If the participant has only completed 6 or less of the questions then the symptom score will be set to missing, unless a subject has only provided responses ‘Yes’ to all of the answered

questions (then it is assumed that the subject only noted the pertinent symptoms for that day). In case of missing severity rate and the answer was ‘yes’ the rate will be imputed by ‘5’.

SIC Analysis Approach Two: Composite Scoring

For the purpose of computing the SIC composite scores, the 25 SIC symptom items with severity ratings (part 1) are scored such that item scores range from 0 (“No,” i.e., not experienced; or “None”) to 10 (“Worst possible”). Except for the Sensory score, SIC composite scores are computed as the average of the symptom severity ratings for each set of items (Constitutional [where C7 = 0 if NO, 10 if YES], Gastrointestinal, Musculoskeletal, Neurological, Respiratory, Upper Respiratory, Lower Respiratory). The average composite score is a number between 0 and 10 (inclusive). Because all SIC composite scores are in the same metric as the item-level severity ratings, this links the interpretation of the SIC composite scores to the items, with higher scores reflecting worse symptoms.

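### Two scoring rules for the exploratory SIC symptom scores need correcting: the Part 3 coding runs backwards, and the divisor for sparse all-Yes days in Part 1 conflicts with the assumption behind keeping them

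*SAP*

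**What the plan says.** SAP section 5.8.4.1, Analysis Approach One, defines the Part 1 scale this way: "Part 1 (25 symptoms): Each symptom is present or absent (0), and if present rated on a 10 point scale", from 0 to 10. The daily symptom score "is the mean score of all items on the SIC for each day, during the COVID-19 episode", and the peak symptom score "is the maximum of all the symptom scores during the COVID-19 episode". An AUC over the episode is also taken.

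Note 1 gives the missing-data rule for Part 1. In general, "total scores will be calculated based on the number of assessments completed by the participant per day". A score is missing when more than 75% of its items were not collected. The worked example says that with 7 or more of 25 answers the mean of the available answers is used, and that with 6 or fewer the score is missing. There is one exception to missing: if all the answers given are Yes, the day is kept, and "then it is assumed that the subject only noted the pertinent symptoms for that day". A Yes without a rating is imputed as 5.

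For the yes/no symptoms the SAP states: "Part 3: Each of the 3 specific symptoms is either present (1) or absent (2"). The specific symptom score is the mean of these codes over the episode. The total specific reported symptom score is the same mean over days with at least one specific symptom.

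Approach Two describes its composites as running "with higher scores reflecting worse symptoms". It codes shaking (C7) as 0 for No and 10 for Yes, and the Sensory score as 0, 5 or 10.

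The section opens with: "The SIC has a total of 30 items assessing signs and symptoms of COVID-19".

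**The concern.** The Part 3 score runs in the opposite direction to every other symptom score in the section. A table of mean differences that places it beside Part 1 and the composites invites a reader to take a higher value as worse, when here it means fewer symptoms.

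The Part 1 exception rests on an assumption that fixes the value of the blank items: if the participant recorded only what was present, the rest were absent and score 0. The only general divisor in the note ignores those zeros. The exception names no other divisor, so the programmer has to choose between two results that differ several-fold.

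Section 5.6.1.3 uses the section 5.8.4 scores to compare symptom severity in infected participants between vaccine and placebo, with tabulated mean differences. The comparison is exploratory, but it should not depend on an unstated programming choice or on a reversed code.

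**Working it through.** **The SAP's own cut-off.** With k of 25 items answered, the missing share is (25 − k)/25. For k = 6 it is 19/25 = 76%, above 75%, so the score is missing. For k = 7 it is 18/25 = 72%, so the day is scored. The cut-off in Note 1 is reproduced.

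**Part 3.** Inputs: three symptoms, present = 1, absent = 2, score = mean (section 5.8.4.1). With m symptoms present, the SAP's score is (m × 1 + (3 − m) × 2)/3. With 0/1 coding it is m/3.

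| Symptoms present | SAP coding | 0/1 coding |
|---|---|---|
| 0 | 2.00 | 0.00 |
| 1 | 1.67 | 0.33 |
| 2 | 1.33 | 0.67 |
| 3 | 1.00 | 1.00 |

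**Part 1, sparse all-Yes day.** Let k items be answered, all Yes, at severity s. Dividing by the answered items (general rule of Note 1) gives s. Scoring the blanks 0 (the stated assumption together with absent = 0) gives k × s/25. The ratio is 25/k. At s = 5, which is also the imputed value for an unrated Yes:

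| k | Divided by answered items | Blanks scored 0 | Ratio |
|---|---|---|---|
| 1 | 5.0 | 0.20 | 25 |
| 2 | 5.0 | 0.40 | 12.5 |
| 3 | 5.0 | 0.60 | 8.3 |
| 6 | 5.0 | 1.20 | 4.2 |

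**If the exception is zero-filled.** Six Yes answers at severity 5 give 30/25 = 1.2. Seven give 35/7 = 5.0, because for 7 or more answers the SAP explicitly uses the mean of the available answers. One more symptom of the same severity raises the score about four-fold.

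**Effect on the peak (assumed values, for illustration).** Suppose the worst fully completed day has 15 symptoms at severity 6: 15 × 6/25 = 3.6. A second day has only two answers, both Yes at severity 5. Divided by the answered items, that day scores 5.0 and becomes the peak. Divided by 25, it scores 0.4 and the peak stays 3.6.

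**Item count.** 25 rated items + 1 temperature + 3 yes/no items = 29, against the stated 30. The items listed under Approach Two (7 constitutional, 5 gastrointestinal, 3 musculoskeletal, 5 neurological or sensory, 9 respiratory) also total 29.

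**The case against.** The strongest objection concerns Part 1. The SAP ties the mean of the available answers to days with 7 or more answers. For 6 or fewer it says only that an all-Yes day is not set to missing, and why. Taken with the definition of the score as a mean over all items, that can be read as zero-filling. This stands: the exception does not state that sparse days are divided by the answered items. It does not remove the fault, because zero-filling only below the cut-off produces the jump from 1.2 to 5.0 shown above.

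On Part 3, the 1/2 code loses no information and reverses exactly, and the sentence on direction is written for the composites. Both points stand. They limit the consequence but do not justify the code. Only the specific symptom score and the total specific reported symptom score are reached. Durations are unaffected, and no Part 3 peak is defined.

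A reader might infer that the mildest diary days receive near-maximal scores. They do not: on the literal reading a sparse all-Yes day scores its mean rated severity, so a single Yes rated 1 scores 1.0. A reader might also infer that vaccine-arm severity is inflated. That would require sparse all-Yes days to differ between arms, and the SAP gives neither their frequency nor their distribution.

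The missing thirtieth item could be a fourth yes/no symptom, such as red or bruised feet or toes, which sections 5.2.4.1 and 5.2.4.2 list. The SAP gives no response format for it, so that identification cannot be made from this document.

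**Conclusion.** Both rules should be corrected. The Part 3 coding is stated plainly and gives a score in the wrong direction, from 2.00 with no symptom to 1.00 with three. The Part 1 exception has no stated divisor of its own. Under the general rule, a sparse all-Yes day scores 4.2 times (six answers) to 25 times (one answer) what the note's own assumption implies. Under zero-filling, the score jumps between six and seven answers.

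The reach is limited. The Part 1 fault touches the daily score, AUC and peak only for participants who have such days, and it sets the peak only when the day exceeds every fuller one. It would therefore be too strong to say that symptom and peak scores are wrong in general. The SIC scores are exploratory and summarised descriptively (sections 5.6.1.3 and 5.8.4.2), and no primary or confirmatory result depends on them. The ratios are exact arithmetic from the SAP's rules; the severities of 5 and 6 and the peak example are illustrative. No direction of bias between arms can be claimed.

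**What to change.** - **Part 3:** code present = 1 and absent = 0.
- **Part 1, Note 1:** state that on any day when every answered item is Yes, unanswered items are scored 0 and the divisor is 25, whether 6 or fewer or 7 or more were answered. Six and seven Yes answers at severity 5 then score 1.2 and 35/25 = 1.4.
- **Sensitivity summary:** repeat the Part 1 scores leaving out sparse all-Yes days, and report how many such days there are by arm.
- **Item count:** reconcile the stated 30 items with 29 against the instrument, and say how any further item is scored.

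The cost is a few lines of SAP wording and scoring code, with no new data. There is a downside to state openly. Days with at least one No are still averaged over the answered items, so a discontinuity remains between all-Yes and mixed days: six Yes answers at severity 6 score 36/25 = 1.44, and adding one No gives 36/7 = 5.14. Participants who skipped items at random on an all-Yes day will also score lower than they should. The sensitivity summary shows how much the handling of sparse all-Yes days matters.

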5.8.4.2. Analysis Methods

SIC scores will be analyzed for participants with any COVID-19 episode based on the PP set.

For continuous variables, number of observations, mean, standard deviation, median, first and third interquartile will be tabulated and means with standard errors will be graphically presented per vaccine regimen and means with standard errors per group and time point (starts since onset of COVID-19 episode). Counts will be tabulated.

These analyses will also be summarized by COVID-19 for each classification (mild, moderate, severe-critical cases) and additionally in a cumulative fashion (at least mild, at least moderate, and all symptomatic cases).

Subgroup analysis may be explored.

5.9. Interim Analyses

Interim analyses are performed in the form of continuous monitoring and are provided in [Table 10](#). No other interim analyses are planned.

Table 10 Specification of Sequential Statistical Analyses

Parameter	Population	Hypothesis	Statistical Method	Criterion	Monitoring Plan
Potential Harm ^a of Symptomatic Cases	FAS	$H_0: VE \geq 0\%$ vs. $H_1: VE < 0\%$	Exact 1-sided binomial test of the fraction of infections assigned to receive the vaccine.	Constant p-value cut-off controlling α at 5%	After every event starting from the 12 th event ^b
Potential Harm ^a of Severe Cases	FAS	$H_0: VE \geq 0\%$ vs. $H_1: VE < 0\%$	Exact 1-sided binomial test of the fraction of infections assigned to receive the vaccine.	one-sided p-value compared to α at 5%, no multiplicity adjustment	After every event starting from the 5 th event
Non-efficacy	PP	$H_0: VE \geq 40\%$ vs. $H_1: VE < 40\%$	Exact 95% CI	Upper limit of the 95%CI < 40%	Every week, starting from the 20 th event after 14 days post dose 1 (Day 15) ^b
Efficacy ^c	PP	$H_0: VE \leq 30\%$ vs. $H_1: VE > 30\%$	Sequential probability ratio test	Controlling the family-wise error rate α at 2.5%	Starting from the 42 nd event 14 days post dose 1 are observed, then at least weekly thereafter ^c
Efficacy ^c	PP	$H_0: VE \leq 30\%$ vs. $H_1: VE > 30\%$	Sequential probability ratio test	Controlling the family-wise error rate α at 2.5%	Starting from the 42 nd event 28 days post dose 1 are observed, then at least weekly thereafter ^c

CI = confidence interval; FAS = full analysis set; PP = per protocol; VE = vaccine efficacy.

^a Harm in the form of an increased rate of symptomatic COVID-19 events due to vaccination.

^b Monitoring stops when the primary efficacy analysis is triggered.

^c The monitoring can only start as soon as the conditions outlined in Section [5.4.1](#) are met.

All boundaries will be monitored by the Statistical Support Group (SSG). If a boundary has been crossed, then the SSG immediately informs the Chair of the DSMB through secure communication procedures. At this point the DSMB will convene, evaluate the totality of the data and provide a recommendation to the Sponsor.

The study team is responsible for providing the blinded information to the SSG. For relevant definitions regarding a case assignment, see Section [5.2](#).

5.9.1. Assigning cases for continuous monitoring

Definitions and general case assignment rules are described in Section [5.2](#).

For continuous monitoring the order of cases will be based on the *onset of symptoms*. An episode of COVID-19 may however start with mild symptoms and may deteriorate to a degree that it satisfies a more severe classification. To avoid situations that an event occurs that already should have been analyzed as based on the onset of symptoms, the approach chosen here is that each case will be analysis-ready at the latest at **Day 15** (see also CTP Section 8.1).

For this approach it is of concern if an event is not resolved at Day 15, AND if that event worsens in severity after analysis-ready status. In the rare case that this happens AND affects one of the 4 monitoring processes, the case will be added to the first upcoming monitoring analysis based on the moment it is established that it satisfies a more severe definition.

Continuous monitoring will be performed on analysis-ready cases known up to that and including that calendar Day; if multiple cases are analysis-ready on a Day, the boundary will be verified for the total number of cases.

For the monitoring of potential severe harm, the event will be entered in the monitoring as soon as the event becomes confirmed as satisfying the severe/critical case definition (from Amendment 5 of the SAP, only severe/critical cases as adjudicated by the Clinical Severity Adjudication Committee will be used in the severe harm monitoring).

The period to define analysis ready- for an episode of COVID-19 to take its course is chosen as it is expected to have limited impact on case classification, and it also allows to assess critical information that is required to determine if the case is part of a continuous monitoring process (and how it should be entered):

- Was the participant included in the FAS? (Note that this means that the participant was randomized and treated.)
- Was the participant treated with the assigned treatment? (Note that if not, the participant would be analyzed *as treated* in the FAS and excluded from the PP population.)
- Was the volume of the injection sufficient ($\geq 80\%$) according to the drug administration log?
- Was the participant seronegative at baseline?
- Was the participant part of the PP population (see Section [4](#))?
- Was the onset of symptoms after double-blind vaccination (Day 2 or later)?
- Was the onset of symptoms after Day 14 (Day 15 or later) or Day 28 (Day 29 or later)?

[figure not shown]
5.9.2. Harm monitoring for excess symptomatic COVID-19 cases

Continuous monitoring for vaccine-associated *enhanced* COVID-19 will be performed based on *symptomatic* COVID-19 events in the FAS population. Only cases where the onset of symptoms is on Day 2 or later will be included. Monitoring for harm will be performed on a daily basis on analysis-ready cases only.

The monitoring starts when there are in total 12 analysis-ready symptomatic cases observed and will continue to be monitored on each calendar day until the primary analysis is triggered. In order to calculate the boundaries for this monitoring while controlling overall alpha level as specified (i.e. 5% overall alpha) an assumption must be made on maximum number of looks that will have to be made. For this purpose, it is assumed that there will be a maximum of 200 symptomatic cases in the FAS before the primary analysis is triggered. This leads to the following boundaries on the number of events in the placebo treatment group for each total number of events. Starting at 12 analysis-ready cases, the boundary is crossed if there are 0 or 1 analysis-ready cases on placebo and all other cases are on active treatment. If there are 2 analysis-ready cases on placebo, the boundary is crossed if the total is 14 cases (i.e., 12 on active), etcetera (Table 11). The boundary is illustrated graphically in Figure 4.

Table 11 The number of Symptomatic Cases on Placebo and Total number of Symptomatic Cases at which Point the Boundary is Crossed (FAS)

Placebo	Total	Placebo	Total	Placebo	Total	Placebo	Total
≤1	12	22	65	43	113	64	160
2	14	23	67	44	115	65	162
3	17	24	69	45	118	66	164
4	20	25	72	46	120	67	167
5	23	26	74	47	122	68	169
6	25	27	76	48	124	69	171
7	28	28	79	49	127	70	173
8	31	29	81	50	129	71	175
9	33	30	83	51	131	72	178
10	36	31	86	52	133	73	180
11	38	32	88	53	136	74	182
12	41	33	90	54	138	75	184
13	43	34	93	55	140	76	186
14	46	35	95	56	142	77	189
15	48	36	97	57	144	78	191
16	50	37	99	58	147	79	193
17	53	38	102	59	149	80	195
18	55	39	104	60	151	81	197
19	58	40	106	61	153	82	200
20	60	41	109	62	156		
21	62	42	111	63	158		

Figure 4 Harm Monitoring Boundary - Active versus Total Number of Symptomatic Cases (FAS)

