3.5.3. Asymptomatic infections and all infections (including asymptomatic)

Based on assumptions prior to unblinding the cases in the placebo group were assumed to be distributed as follows: 45% asymptomatic cases and 55% symptomatic cases of which 20% were mild infections, and 60% were moderate and 20% were severe infections, according to the case definitions. Based on a VE as detailed in [Table 4](#), events were simulated according to a binomial distribution and the primary endpoints evaluated against the SPRT boundary.

Upon crossing the SPRT boundary, the power against asymptomatic or undetected infections as well as against the evaluation of all infections was calculated (null hypothesis $VE>0$). The alpha level for that evaluation was adjusted according to the procedure detailed in the statistical hypothesis evaluation.

The results are based on 1000 simulations. The powers presented are not conditional on passing the first 2 secondary hypotheses.

Table 4 Powers for Asymptomatic and All Infections for various Fractions of available N-Elisa samples at 2.5 months at the time of analysis

Fraction of available N-Elisa samples At 2.5 months	Vaccine efficacy			Power		
	Moderate/Severe	Mild	Asymptomatic	Moderate/Severe	Asymptomatic	All infections
100%	70%	60%	30%	99%	14%	96%
100%	70%	60%	40%	99%	28%	99%
100%	70%	60%	50%	99%	47%	>99%
50%	70%	60%	30%	99%	4%	99%
50%	70%	60%	40%	99%	7%	>99%
50%	70%	60%	50%	99%	13%	>99%

This is based on the protocol assumed incidence of 1.4% during 3 months and waning thereafter (by 50% in Month 4, by 62% in Month 5 and beyond) and a sample size of 60,000.

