4. POPULATIONS (ANALYSIS SETS) FOR ANALYSIS

Vaccine assignment will be analyzed according to an as-treated principle. The analysis sets that are used for the various analyses are described in [Table 5](#).

Table 5 Analysis Sets

Analysis Sets	Description
Enrolled	The enrolled analysis set includes all participants who signed the ICF and who were not screen failures
Randomized	The randomized analysis set includes all participants who were randomized in the study.
Full Analysis Set (FAS)	All randomized participants with a documented study vaccine administration, regardless of the occurrence of protocol deviations and serostatus at enrollment.
Per Protocol Efficacy Set (PP; primary efficacy analysis set for vaccination studies)	Participants in the FAS who received double-blind study vaccine and who were seronegative at the time of double-blind vaccination and who have no major protocol deviations that were judged to possibly impact the efficacy of the vaccine. Participants who became aware of their study vaccine allocation will cease to be part of the PP population. See below for a definition.
Per Protocol Immunogenicity Analysis Set (PPI)	All randomized and vaccinated participants, including those who are part of the Immuno Subset and for whom immunogenicity data are available, excluding participants with major protocol deviations expected to impact the immunogenicity outcomes. In addition, for participants who experience a SARS-CoV-2 event (molecularly confirmed), samples taken after the event and samples taken outside protocol windows will not be taken into account in the assessment of the immunogenicity. The PPI population is the primary immunogenicity population. For key tables, sensitivity immunogenicity analyses will also be performed on the FAS, including participants who are part of the Immuno Subset for whom immunogenicity measures are available. Excluded samples might be taken into account as well in the sensitivity analysis. Analyses of vaccine immunogenicity and immune correlates of risk will be based on PPI.

For the PP the following additional criteria will be applied:

- having received the double-blind vaccine according to the randomization schedule
- having received at least 80% of the scheduled double-blind vaccination volume (according to the administration log)
- met inclusion criteria 1 (informed consent was obtained)

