5.4. Primary Endpoint(s) Analysis

5.4.1. Timepoint of primary analysis

The interim monitoring for the primary analysis can start as soon as the following conditions are met:

1. A minimum of 6 COVID-19 primary endpoint cases for the ≥ 60 years age group with onset at least 28 days after double-blind vaccination

2. At least 42 cases meeting the primary endpoint definition of moderate to severe/critical COVID-19 with onset at least 28 days after double-blind vaccination
3. A subset of at least 5 cases meeting the definition of severe/critical COVID-19 with onset at least 28 days after double-blind vaccination

No interim evaluation will be done, until those conditions are fulfilled. Monitoring for efficacy will not start before the above conditions 1-3 are met.

The efficacy analysis will be triggered by either:

- a) An interim evaluation if all prespecified efficacy boundaries have been met simultaneously at the same calendar timepoint OR if at least 154 cases meeting the primary endpoint definition of moderate to severe/critical COVID-19 are observed for events with onset at least 28 days after double-blind vaccination

AND

- b) The above 3 conditions are met.

OR, alternatively,

If the prespecified non-efficacy has been met (evaluating events with start 14 days after vaccination) or when the harm boundary has been crossed. The decision rules for harm and non-efficacy are detailed in Section [5.9](#)

If an efficacy signal is triggered before the required 8-week follow-up after vaccination of 50% of the enrolled participants is reached, an additional analysis will be performed when that follow-up timepoint is reached. If the time between the efficacy signal and the required 8-week median follow-up is too short to make a difference in terms of preparing two analyses, then a single analysis will take place at the time of the 8-week median follow-up. The analysis at the time of the 8-week median follow-up is considered the primary analysis.

If more than 154 primary endpoints are observed for events with onset at least 28 days after double-blind vaccination before the 3 conditions above are met, a single analysis will take place as soon as the conditions are met, using the full 2.5% one-sided significance level.

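### The symptomatic-harm boundary ends at 200 FAS cases, although the plan's own 154-event trigger lets monitoring run past that count

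*SAP*

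**What the plan says.** Section 5.9.2 monitors all symptomatic cases in the FAS for vaccine-associated enhanced disease, on every calendar day from the 12th case until the primary analysis is triggered. On which cases count: "Only cases where the onset of symptoms is on Day 2 or later will be included". The FAS takes participants "regardless of the occurrence of protocol deviations and serostatus at enrollment" (section 4, Table 5), so seropositive and non-PP participants are counted, as are mild cases.

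The number of looks is fixed by assumption: "it is assumed that there will be a maximum of 200 symptomatic cases in the FAS before the primary analysis is triggered". Table 10 gives the criterion as "Constant p-value cut-off controlling α at 5"%. Table 11 runs from 0 or 1 placebo cases of 12 to 82 placebo cases of 200. Nothing is given for case 201 onward.

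Section 5.4.1 sets the end of monitoring. Unless a boundary is crossed earlier, the primary analysis is triggered "if at least 154 cases meeting the primary endpoint definition of moderate to severe/critical COVID-19 are observed" with onset at least 28 days after vaccination. The section also provides for more than 154 if its minimum-data conditions are met late. For the case mix, section 3.5.3 assumes "55% symptomatic cases of which 20% were mild infections", the rest being moderate (60%) or severe (20%).

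**The concern.** The harm count is much wider than the count that ends monitoring. It adds mild cases, cases with onset on Day 2-28, seropositive participants and participants outside the PP set. A maximum of 200 therefore has to leave room for all of these on top of 154 primary events, and the SAP never reconciles the two figures.

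At stake is a participant-safety rule. If the count passes 200 while monitoring is still required, the statistical support group has no tabulated boundary. It must then either stop a check that the plan requires or improvise one with unblinded data. The 5% calibration was made for looks at 12 to 200 cases only, so it does not cover all the looks that the plan allows.

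**Working it through.** **1. Reproducing Table 11.** Under VE = 0% and 1:1 allocation, each case falls on placebo with probability 0.5. A constant-p rule crosses at *n* cases with *x* on placebo when P(X ≤ x | n, 0.5) is at or below a cut-off *c*.

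- n = 12, x = 1: 13/4096 = 0.0032, crosses.
- n = 13, x = 2: 92/8192 = 0.0112, does not cross.
- n = 14, x = 2: 106/16384 = 0.0065, crosses, as tabulated.

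A cut-off of about 0.00775 reproduces the table at every total from 12 to 200. The same exact recursion applied to the efficacy boundary (Table 13) returns the stated 2.398% type I error and 86.22% power, so the method agrees with the plan's own.

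**2. Error spent, harm rule on its own.** Exact recursion with a look after every case:

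| Total cases | Cumulative one-sided error, cut-off 0.00775 |
|---|---|
| 192 | 4.98% |
| 200 (end of Table 11) | 5.07% |
| 240 | 5.40% |
| 250 | 5.5% |
| 300 | 5.83% |
| 350 | 6.1% |
| 400 | 6.38% |

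With a look at every second case, as a stand-in for pooled daily looks, the figures are 4.6% at 200 and 4.9% at 240. With every third case, the figure is 4.9% at 300.

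**3. Symptomatic cases implied by 154 events.** From section 3.5.3, 80% of symptomatic cases are moderate or severe, so 154/0.80 = 192.5, and 200 − 192.5 = 7.5. The 20% is a placebo-group share. If VE is 60% against moderate/severe disease but lower against mild disease:

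- Placebo moderate/severe: 154/1.4 = 110. Placebo mild: 110 × 0.2/0.8 = 27.5.
- VE against mild 50%: 154 + 27.5 × 1.5 = 195.
- VE against mild 30%: 154 + 27.5 × 1.7 = 201.

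**4. Adding Day 2-28 cases.** Assumptions: the incidences in section 3.1 are annualized and constant, 10% are seropositive and removed, and everyone completes Day 2-28. Early cases = N × 0.9 × incidence × 27/365 × (1 − VE/2), with early VE of 0% or 60%. Total = (154 + early cases)/0.80.

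| N, incidence | Early moderate/severe (VE 60% to 0%) | Symptomatic total at 154 |
|---|---|---|
| 60,000, 1.4% | 39 to 56 | 241 to 262 |
| 40,000, 3.8% | 71 to 101 | 281 to 319 |
| 40,000, 6.3% | 117 to 168 | 339 to 402 |

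Other FAS cases (seropositive, non-PP) come on top.

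**5. When the 200th case arrives.** 200 symptomatic cases correspond to 200 × 0.8 = 160 moderate/severe cases. At the Amendment 3 incidences with early VE 60%, that is 160 − 117 = 43 to 160 − 71 = 89 Day-29 events, well before 154.

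**6. Allowing for other triggers.**

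- True VE 60%: the efficacy boundary, applied from 42 events, crosses by 100 events with probability about 60%. About 20% of trials reach 154.
- VE = 0%: the non-efficacy boundary (Table 12) crosses with probability 72% by 80 events, 81% by 100 and 93% by 154.
- Joint simulation at VE = 0% (40,000 runs for each of two assumed case mixes), with non-efficacy ending monitoring: 10-13% of trials pass 200 cases, the harm rule crosses in 1.7-1.9%, and no run first crosses after 200.
- Same simulation with non-efficacy ignored: about 95% pass 200, and the extended rule crosses in 5.8-5.9%.

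**The case against.** The strongest objection is to a reading that a reader might take from step 2, namely that the stated 5% error fails. The document does not support it.

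- If the rule simply ends at 200, no further alpha is spent and the error is about 5%. Inflation needs an extension that the SAP does not prescribe.
- Table 10 asks for a look after every event, but sections 5.9.1 and 5.9.2 describe daily checks on pooled totals, which lower the error. The 5.07% is close to rounding.
- The error is defined at VE = 0%, where the non-efficacy trigger usually ends monitoring first.

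All of this stands. It leaves open what is to be done at case 201.

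Second, 154 is the latest event-driven efficacy trigger, not the expected one, and sections 3.1 and 5.9.6 anticipate an earlier signal. That is true, but step 5 shows that 200 can be passed well before 154 at the incidences in the same sections.

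Third, the document's own figures give about 193, just below 200. The excess needs early-onset or non-PP cases, whose number is not stated. That is also true, but such cases are counted by definition, and 7 or 8 is very little room for four weeks of onset in about 40,000 participants.

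Fourth, the surveillance loss is limited. Severe-case harm monitoring continues without a case cap (section 5.9.3), and the DSMB sees unblinded data. This bears on how serious the gap is, not on whether it exists.

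Finally, this SAP version postdates the monitoring. That is correct, and it changes the remedy.

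**Conclusion.** The 200-case maximum does not fit the plan's own target of 154 Day-29 PP events, and the harm boundary is undefined from case 201 although monitoring may still be required. The 5% calibration therefore does not cover all the looks that the plan allows.

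The size is modest. With a look at every case and the harm rule on its own, the error is 5.07% at 200 and about 5.5% to 6.4% if the same cut-off is carried to 250-400 cases. It is lower with pooled daily looks, and well under 5% at VE = 0% if the non-efficacy trigger ends monitoring.

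The figure of 192.5 rests only on the document's severity mix. The range of about 241-402 rests on annualized incidence, early VE of 0-60% and constant rates, which are assumptions. The conclusion is a safety boundary with too short a range, not a demonstrated failure of error control.

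**What to change.** Either of two changes would settle it.

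1. **Recompute Table 11 and Figure 4** for a maximum consistent with 154 Day-29 PP events, about 250-400 symptomatic FAS cases under the assumptions above. The constant cut-off that holds 5% is about 0.0068 for 250, 0.0064 for 300, 0.0062 for 350 and 0.0058 for 400. Print the cut-off in the SAP. This costs one recalculation, a longer table and a slightly stricter boundary at low counts. For example, at 0.0064 two placebo cases of 14 (106/16384 = 0.0065) no longer cross, but two of 15 (121/32768 = 0.0037) do.
2. **Because monitoring is complete in this SAP version**, state in section 5.9.2 which rule was applied past 200 cases, the maximum number of symptomatic FAS cases reached before the trigger, and the error actually achieved given the looks taken. If 200 was never passed, one sentence saying so is enough.
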